11.4 Analysis of Vital Signs and Weight

Not applicable; vital signs and weight are not collected in this study.

12.0 Summary of Changes

Table 4. SAP Version History Summary

Version	Date	Summary
1.0	19 August 2019	Original version

The following changes were made between the latest version of the protocol and SAP Version 1.0:

- Under resistance analyses, only listings are planned to be provided due to the limited number of virologic failures treated with ABT-493 and/or ABT-530;
- IL28B is no longer included in resistance listings due to its limited utility in predicting virologic failure;
- The number and percentage of subjects who have new HCV infection (reinfection) will be summarized for all subjects in the full analysis set, rather than for the subset of subjects in the full analysis set who had achieved SVR₁₂ as the outcomes of relapse and maintenance of SVR are of main interest rather than the rate of reinfection

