For all subjects who experience VF (whether before or during enrollment in Study M13-576), a listing by subject of all baseline variants relative to prototypic reference sequence at signature resistance-associated amino acid positions will be provided for each DAA target (NS3 and/or NS5A as appropriate).

For all subjects who experience VF (whether before or during enrollment in Study M13-576), the HCV amino acid sequence as determined by population or deep sequencing at available post-baseline time points (including previous study and Study M13-576) with an HCV RNA level of  $\geq 1000$  IU/mL will be compared to the baseline and appropriate prototypic reference amino acid sequences. A listing by subject and time point of all post-baseline variants detected by population or deep sequencing relative to the baseline amino acid sequences will be provided for each DAA target (NS3/4A and/or NS5A as appropriate). A listing by subject and time point of all post-baseline variants (by population or deep sequencing) at signature resistance-associated amino acid positions relative to the appropriate prototypic reference amino acid sequences will be provided.

The number and percentage of subjects with post-baseline variants at signature amino acid positions by population or deep sequencing, listed by amino acid position and variant within a DAA target at Post-Treatment Week 24, 48 or time points up to Post-Treatment Week 144 (3 years) compared to baseline will be summarized, along with the number of subjects for whom sequence information was obtained for each DAA target and overall. Additionally, the number and percentage of subjects in whom a signature variant persisted at Post-Treatment Week 24, 48 or time points up to Post-Treatment Week 144 (3 years), out of the total number of subjects with that variant at the VF time point and at Post-Treatment Week 24, 48 or time points up to post-treatment Week 144 (3 years) will be summarized by DAA target (NS3 and/or NS5A, as appropriate), and variant. If a signature variant is detectable in a sample by population or deep sequencing at a later time point, then the variant is imputed as being detectable at earlier time windows even if the sample from the earlier time window from that subject is not sequenced.

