If no resistance-associated variants are detected by population or deep sequencing in a given target for a subject either at the time of failure or in a post-treatment sample, then that target may not be sequenced in subsequent samples from that subject.

Time to loss of key resistance-associated variants will be summarized.

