4.1 Objectives

The primary objectives of this study are as follows:

- Assess the durability of response for subjects who achieved SVR₁₂ with a regimen including ABT-493 and/or ABT-530.
- Assess the persistence of specific HCV amino acid substitutions associated with drug resistance in subjects who experienced virologic failure.

The secondary objectives of the study are as follows:

• Summarize medical events related to progression of liver disease including but not limited to events of hepatic decompensation, change in Child-Pugh classification, liver transplantation, hepatocellular carcinoma, and/or death.

• Summarize results of the following laboratory tests and scores: FibroTest, APRI, IP-10, alpha fetoprotein (if collected under a protocol version prior to protocol Amendment 3), FibroScan, and liver biopsy.

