10.3 Resistance Analyses

The following subjects in the full analysis set will have resistance testing conducted: (1) those with on-treatment virologic failure (VF) in the previous study; (2) those with post-treatment relapse prior to enrollment in Study M13-576; and (3) those who become viremic (with HCV) during Study M13-576.

For all subjects entering Study M13-576 who meet the criteria for resistance testing above (i.e., have virologic failure), listings will be provided to summarize HCV subtype, time of VF, HCV RNA levels, time point(s) sequenced, and assessment of possibility of new infection.

Only samples with an HCV RNA level of \geq 1,000 IU/mL will undergo sequence analysis in order to allow accurate assessment of the products of amplification. For subjects who experience VF before or during Study M13-576, the sample closest in time after the failure with an HCV RNA level \geq 1,000 IU/mL will be used if the HCV RNA level at the time of VF is < 1,000 IU/mL.

The regions of interest for next-generation sequencing (NGS) from all evaluated time points in this study are those encoding complete NS3/4A and/or NS5A (based on regimen received in the earlier study). Subtype-specific prototypic reference strains for sequence analyses will be utilized.

For each DAA target, signature amino acid positions and a key subset of amino acid positions are listed in Table 3. Appropriate subtype-specific prototypic reference sequences will be used for comparison with sequences from samples.

[figure not shown]
[figure not shown]

Table 3. Signature Amino Acid Positions and the Key Subset of Amino Acid Positions

Target	Signature Amino Acid Positions	Key Subset of Amino Acid Positions
GT1 NS3	36, 43 (GT1a only), 54, 55, 56, 80, 107, 122, 132 (GT1a only), 155, 156, 158, 168, 170, 175 (GT1b)	155, 156, 168 (all GTs)
GT 2-6 NS3	36, 43, 54, 55, 56, 80, 155, 156, 166 (GT3 only), 168	-
GT1 NS5A	24, 28, 29, 30, 31, 32, 54 (GT1b only), 58, 62, 92, 93	24, 28, 30, 31, 58, 92, 93 (all GTs
GT 2-6 NS5A	24, 28, 29, 30, 31, 32, 58, 92, 93	-

The following definitions will be used in the resistance analyses:

- Baseline sample: sample collected before the first dose of DAA study drug in the previous study.

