- Baseline polymorphism: a polymorphism by NGS in a baseline sample (≥ 2% or ≥ 15% prevalence within a subject's viral population depending on polymorphism frequency threshold utilized) that was not present in the appropriate prototypic reference amino acid sequence for a given DAA target (NS3/4A or NS5A).
- Polymorphism/substitution at a signature amino acid position: polymorphism (relative to reference) present in a baseline sample or substitution (relative to baseline) present in post-baseline sample at a signature amino acid position.
- Post-baseline substitution: an amino acid substitution in a post-baseline time point sample that was not detected at baseline (< 2%) in the subject and is detectable in ≥ 2% of the sequences from the post-baseline sample.
- Enriched substitution: substitution present in both the baseline and a post-baseline sample whose prevalence in the post-baseline sample is at least 20 percentage points greater than the prevalence in the baseline sample [(post-baseline % baseline %) ≥ 20].
- Treatment-emergent substitution: A post-baseline substitution or an enriched substitution.

• Substitution at signature amino acid position: Substitution in a post-baseline sample observed at ≥ 2% prevalence within a subject's viral population that was not present in the appropriate prototypic reference amino acid sequence for a given DAA target (NS3/4A or NS5A).

For subjects with virologic failure who have resistance testing conducted:

- A listing by subject of all baseline polymorphisms (2% detection threshold) at signature amino acid positions will be provided for each DAA target (NS3/4A and NS5A).
- A listing by subject and time point of all treatment-emergent substitutions relative to the baseline amino acid sequences will be provided for each DAA target (NS3/4A and NS5A).
- A listing by subject and time point of all post-baseline substitutions at signature amino acid positions relative to the appropriate subtype-specific reference amino acid sequence will be provided for each DAA target (NS3/4A and NS5A).

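### SAP 10.3 would list in-study reinfections as virologic failures with treatment-emergent substitutions, and it plans no summary of persistence, a primary objective

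*SAP*

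**What the plan says.** **Objective.** SAP 4.1 keeps as a primary objective: "Assess the persistence of specific HCV amino acid substitutions associated with drug resistance in subjects who experienced virologic failure". Protocol 4.0 has the same objective, and Protocol 5.3.3 makes persistence the primary resistance outcome.

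**Planned summaries.** Protocol 8.1.2 promises, by post-treatment week up to Week 144, "the number and percentage of subjects in whom a signature variant persisted", with the denominator "out of the total number of subjects with that variant at the VF time point and at Post-Treatment Week 24, 48" or a later week. It also promises a summary of time to loss. A variant detected later is imputed as present in earlier windows. Once a target shows no resistance-associated variant, "then that target may not be sequenced in subsequent samples from that subject". SAP 10.3 contains neither summary, and SAP 12.0 states that "only listings are planned to be provided due to the limited number of virologic failures treated with ABT-493 and/or ABT-530".

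**Who is tested and what is listed.** SAP 10.3 tests on-treatment failures from the previous study, relapses before enrollment, and "those who become viremic (with HCV) during Study M13-576". It then describes the listed subjects as those who "meet the criteria for resistance testing above (i.e., have virologic failure". For them it plans "A listing by subject and time point of all treatment-emergent substitutions relative to the baseline amino acid sequences". A post-baseline substitution is one below 2% at baseline and at 2% or more later; every such substitution counts as treatment-emergent.

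**Reinfection.** SAP 10.1 defines reinfection by a different genotype, subtype or clade from baseline and excludes it from every relapse definition.

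**The concern.** The resistance section does not carry over the split between relapse and reinfection that the efficacy section makes. A reinfecting virus is a different strain from the one treated in the previous study. Comparing it with the pre-treatment virus yields differences that drug pressure did not select, yet the listing would call them treatment-emergent. Someone using the listing to describe the resistance profile of ABT-493 or ABT-530 could attribute them to the drug.

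The second matter is that one of two primary questions, how long resistance substitutions persist, has no planned summary. Readers would have to build one from listings and choose their own rule for time points with no sequence. Such a gap can mean that the variant was gone and the target was not sequenced again, that HCV RNA was below 1,000 IU/mL, or that the visit was missed. The failure listing shows HCV RNA levels and the time points sequenced, which helps, but SAP 10.3 gives no rule for treating these cases.

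**Working it through.** The documents state no persistence figure, number of failures, reinfection rate or sample size calculation, so there is no plan figure to reproduce. The text comparison rests on the documents; the numerical inputs below are assumptions.

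**1. Does a reinfection reach the treatment-emergent listing?**
- Arising during the study: the subject becomes viremic, meets the third testing criterion, is called a virologic failure, and, if HCV RNA is at least 1,000 IU/mL, is sequenced and compared with baseline. The definition has no same-strain condition, so the answer is yes.
- Arising before enrollment: the first two criteria cover on-treatment failure and relapse, and SAP 10.1 excludes reinfection from relapse. The answer is no.

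**2. How likely is a spurious entry?** Suppose the new strain differs from the baseline virus at each signature position with probability d, independently. Over m positions, P(at least one) = 1 − (1 − d)^m. SAP Table 3 gives 9 positions for NS5A in genotypes 2 to 6; 20 is roughly both targets together.

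| m | d = 2% | d = 5% | d = 20% |
|---|---|---|---|
| 9 | 1 − 0.98^9 = 17% | 37% | 87% |
| 20 | 1 − 0.98^20 = 33% | 64% | 99% |

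The listing is not confined to signature positions, so the chance of any entry is higher.

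**3. Could the protocol's percentage simply be restored?**
- Literal reading: the denominator is subjects with the variant at failure and again at week w. All of them have the variant at week w, so numerator equals denominator and the result is 100% whatever the truth.
- Reading the denominator as subjects with the variant at failure who were sequenced at week w, with the stop rule always used: those already negative have left, so the figure estimates the chance of keeping the variant since the previous visit. With a constant loss rate and six 24-week visits, that is S^(1/6), where S is true persistence at Week 144: 0.20^(1/6) = 76%, 0.50^(1/6) = 89%, 0.80^(1/6) = 96%. A simulation of 300,000 subjects under these assumptions gave the same values. With 30% of samples missed it gave 66%, 84% and 95%.
- Same reading with the stop rule never used: the simulation returned 20%, 50% and 80% at Week 144, so there was no bias there. With 30% missed samples, the backward imputation raised earlier weeks by about 1 to 6 points.
- Small example: of 20 subjects with a variant at failure, 10, 8 and 6 carry it at Weeks 24, 48 and 96. Sequenced-only figures are 10/20 = 50%, 8/10 = 80% and 6/8 = 75%. With all 20 retained they are 50%, 8/20 = 40% and 6/20 = 30%. This assumes no drop-out or re-treatment, that every loss clears the whole target, and that the stop rule is always used.

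**4. How precise would a reported proportion be?** Exact (Clopper-Pearson) 95% intervals for assumed numbers of failures: 2/5 gives 5% to 85%; 5/10, 19% to 81%; 10/20, 27% to 73%; 20/40, 34% to 66%.

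**The case against.** **Persistence.** The change from the protocol is declared and a reason is given. The study is purely descriptive, with no hypothesis test. Listings by subject and time point remain, and with few failures a percentage says little. All of this is correct. A reader might infer that the trial cannot say how long resistance lasts; the documents do not support that, because persistence can be read case by case where samples were sequenced. What survives is that small numbers explain a wide interval or a bare n/N, not the absence of any summary of a primary objective. SAP Table 1 already provides post-treatment windows for resistance endpoints, and SAP Table 3 names a key subset of positions that no output in SAP 10.3 uses.

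**The protocol's denominator.** A reader might infer that a planned result is built to come out near 100%. It is not: the SAP drops that percentage. The 100% follows only from the literal wording. The upward bias under the other reading needs the stop rule, which is optional and applies only when the target shows no resistance-associated variant at all. This therefore limits how a summary may be reinstated and is not a flaw in a planned output.

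**Reinfection.** A reader might infer that all reinfections are processed as failures and distort resistance rates. The text does not go that far. Reinfections before enrollment are outside the criteria; the failure listing carries an assessment of possible new infection; SAP 10.2 separates relapse from reinfection; and with listings only there is no rate to distort. Newly viremic subjects must also be sequenced, because reinfection is identified mainly by phylogenetic analysis. What stands is that the new-infection assessment is specified for the failure listing and not for the treatment-emergent listing, where the label would be wrong.

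**Conclusion.** Two defects in SAP 10.3 hold on the text.

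First, followed as written, it labels in-study reinfections as virologic failures and lists their differences from the pre-treatment virus as treatment-emergent, in conflict with SAP 10.1. The scope is narrow: only reinfections arising during the study, and only listings. For each such subject at least one wrong entry at a signature position is plausible to near certain (17% to 99% over the assumed ranges). The number of such subjects is not given.

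Second, a primary objective has no planned summary of persistence or time to loss. The omission is disclosed and partly offset by the listings, so what is lost is a stated answer, not the underlying data. The summary would be imprecise: even 10/20 carries an interval of 27% to 73%.

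The 76%, 89% and 96% figures rest on a constant loss rate, one variant per target, no missed samples and the stop rule always applied. They show why the protocol's denominator should not be reused as worded; they do not forecast any reported result.

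**What to change.** In SAP 10.3:

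1. Keep viremia during the study as a trigger for sequencing, but limit the treatment-emergent listings to subjects not classified as reinfected under SAP 10.1. List reinfected subjects separately, against the subtype-specific reference sequence only. Keep the new-infection assessment in the failure listing.
2. Add one descriptive table per DAA target: n/N (exact interval optional) with a key-position treatment-emergent substitution present at failure and still detected at windows such as Post-Treatment Weeks 24, 48, 96 and 144. N is the subjects with it at failure who are still followed and not re-treated. Count a target not re-sequenced after a negative result as lost, and show separately the number whose status in the window is unknown.
3. Add a descriptive time from failure to loss, censored at the last sequenced sample or at re-treatment.
4. Do not reinstate the Protocol 8.1.2 denominator as worded. Amend SAP 12.0 to match.

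The cost is SAP wording, one extra listing, and one small table with a time-to-loss summary from data already sequenced. The downside is small N and wide intervals, which showing n/N makes plain.
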